9.2.2 Primary endpoint(s) analyses

The primary endpoint will be analyzed in mITT population.

The primary endpoint is the proportion of participants achieving remission without requiring TPE during the overall study period. Remission is defined as sustained Clinical Response with either (a) no TPE and no anti-VWF therapy for ≥ 30 days (Clinical Remission) or (b) with attainment of ADAMTS13 activity level $\geq 50\%$ (Complete ADAMTS13 Remission), whichever occurs first. Remission is assessed starting from the clinical response (for participants not requiring TPE) or the end of TPE (for participants requiring TPE), until the end of study.

Clinical response is defined as sustained platelet count $\geq 150 \times 10^9/L$ and LDH $< 1.5 \times$ ULN and no clinical evidence of new or progressive ischemic organ injury for at least 2 consecutive visits.

Clinical remission is defined as sustained Clinical Response with no TPE and no anti-vWF therapy for ≥ 30 days.

Complete ADAMTS13 Remission is defined as sustained Clinical Response with attainment of ADAMTS13 activity level $\geq 50\%$ for at least 2 consecutive visits during the overall study period.

Responders are participants who achieve remission without requiring TPE during the overall study period. Each participant will be classified as a responder or non-responder per the response criteria, and the proportion of responders will be calculated together with a 95% Wilson CI.

9.2.3 Secondary endpoint(s) analyses

Secondary endpoints are listed in [Table 2](#).

Secondary efficacy endpoints analyses are defined in this section. Secondary safety endpoints analyses are defined in [Section 9.2.6.1](#) (AE, SAE, AESI), and [Section 9.2.6.2](#) (clinical safety laboratory variables, vital signs, and ECG).

All secondary endpoints will be analyzed using descriptive statistics, frequency, percentage, and CIs as appropriate. The time to event endpoints will be analyzed using a Kaplan-Meier analysis.

The following secondary efficacy endpoints will be analyzed in mITT population and summarized using the count and percentage of participants. Two-sided 95% confidence intervals (CIs) will be provided.

- Proportion of participants achieving Remission during the overall study period
- Proportion of participants who require TPE during the on-treatment period
- Proportion of participants achieving Clinical Response during on-treatment period and during the overall study period
- Proportion of participants refractory to therapy during the on-treatment period
- Proportion of participants with TTP-related death during the on-treatment period and during the overall study period
- Proportion of participants with a clinical exacerbation of iTTP during the on-treatment period and during the overall study period
- Proportion of participants with a clinical relapse of iTTP during the on-treatment period and during the overall study period

Time to platelet count response will be analyzed in mITT population and analyzed using a Kaplan-Meier analysis. Median time to event (with two-sided 95% CIs) will be reported.

Selected efficacy endpoints may be summarized in ITT population.

9.2.5 Multiplicity adjustment

All analyses will be descriptive in nature and therefore adjustments for multiplicity will not be applied.

9.2.6 Safety analyses

All safety analyses will be performed on the Safety population.

9.2.6.1 Adverse events

All adverse events will be coded using the version of Medical Dictionary for Regulatory Activities (MedDRA) in effect at Sanofi at the time of database lock.

The AEs will be analyzed in the following 3 categories:

- Pre-treatment AEs: AEs that developed, worsened or became serious during the pre-treatment period.
- TEAEs: AEs that developed, worsened or became serious during the treatment-emergent period
- Post-treatment AEs: AEs that developed, worsened or became serious during the post-treatment period

The primary focus of adverse event reporting will be on TEAEs. Pre-treatment and post-treatment adverse events will be described separately.

Safety will be assessed through descriptive summaries of AEs, SAEs, and AESIs during the TE period. The incidence of AEs will be summarized by system organ class and preferred term. The AE summaries will be generated with number (%) of participants experiencing at least one event.

9.2.6.2 Clinical safety laboratory variables, vital signs and electrocardiograms (ECGs)

Clinical safety laboratory variables, vital signs and electrocardiogram (ECG) variables will be analyzed in the Safety population.

[figure not shown]
For clinical safety laboratory variables and vital signs, descriptive statistics for results and changes from baseline will be provided by time point during the on-treatment period. Clinical safety laboratory variables and vital signs will be converted into standard international units.

For ECG, the incidence of participants with at least one abnormal ECG during the treatment-emergent period will be summarized regardless of the baseline level and according to the following baseline status categories:

- Normal/missing
- Abnormal

9.2.6.3 Product complaints

Product complaints will be summarized in the Safety population. Product complaint summaries during the on-treatment period will be summarized using the count and percentage of participants experiencing at least one event.

9.3 INTERIM ANALYSES

An interim analysis will be performed after the first 30 participants with baseline ADAMTS13 activity <10% have completed treatment period and 12 weeks of follow-up.

The SAP will describe the planned interim analyses in greater detail.

9.4 SAMPLE SIZE DETERMINATION

The primary endpoint is the proportion of participants achieving Remission without requiring TPE during the overall study period. The responder rate will be estimated, and no pre-specified success criterion and formal statistical hypothesis testing is planned.

An adequate number of participants will be enrolled to ensure at least 55 participants with ADAMTS13 activity levels <10% at baseline are available for analysis of the primary endpoint. It is anticipated that approximately 61 participants will be enrolled in the study.

With the sample size of 55, assuming the true responder rate of participants who achieve remission without requiring TPE during the overall study period is 70% (ie, overall, 85% remission rate and 18% of participants requiring TPE), the lower bound of 95% Wilson CI would be 58% ([Table 7](#)).

Table 7 - Lower bound of 95% Confidence Interval given various assumed rates of participants achieving Remission without requiring TPE during the overall study period

Assumed responder rate	Lower bound of 95% CI of responder rate ^a
65% or below	At most 52%
70%	58%
75%	64%
80%	68%
85% or greater	At least 74%

^a In post-hoc analysis of HERCULES, the upper confidence limit of remission rate for the placebo arm (placebo + IST + TPE) was 54%.

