4 SAMPLE SIZE DETERMINATION

The primary endpoint is the proportion of participants achieving remission without requiring TPE during the overall study period. The responder rate will be estimated, and no pre-specified success criterion and formal statistical hypothesis testing is planned.

An adequate number of participants will be enrolled to ensure at least 55 participants with ADAMTS13 activity levels of <10% at baseline is available for analysis of the primary endpoint (mITT analysis).

With the sample size of 55 participants, assuming the true responder rate of participants who achieve remission without requiring TPE during the overall study period is 70% (ie, overall, 85% remission rate and 18% of participants requiring TPE), the lower bound of 95% Wilson confidence interval (CI) would be 58%.

Table 6 - Lower bound of 95% confidence interval given various assumed rates of participants achieving Remission without requiring TPE during the overall study period

Assumed responder rate	Lower bound of 95% Confidence Interval of responder rate*
65% or below	At most 52%
70%	58%
75%	64%
80%	68%
85% or greater	At least 74%

* In post-hoc analysis of HERCULES, the upper confidence limit of remission rate for the placebo arm (placebo + IST + TPE) was 54%. HERCULES (ALX0681-C301) was a Phase III, randomized, double-blind, placebo-controlled, study to evaluate the efficacy and safety of caplacizumab when administered in addition to standard of care treatment in subjects with an acute episode of acquired TTP.

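### The Wilson lower bounds that justify n=55 rest on an unstated rounding-up of the responder count: the 75% row should read 62%, not 64%, and 58% belongs to an observed 39/55, not to a true rate of 70%

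*Protocol*

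**What the plan says.** Protocol section 9.4 sets the analysis size so that "at least 55 participants with ADAMTS13 activity levels <10% at baseline are available for analysis of the primary endpoint". It adds "It is anticipated that approximately 61 participants will be enrolled in the study", but the stated precision refers to 55, not 61. The planning rate is introduced with "assuming the true responder rate of participants who achieve remission without requiring TPE during the overall study period is 70" per cent, explained as "ie, overall, 85% remission rate and 18% of participants requiring TPE", and the sentence concludes that "the lower bound of 95% Wilson CI would be 58" per cent. SAP section 4 repeats it ("the lower bound of 95% Wilson confidence interval (CI) would be 58" per cent), as does the synopsis in Protocol section 1.1.

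Protocol Table 7 and SAP Table 6 are identical in content. Against assumed responder rates of 65 (or below), 70, 75, 80 and 85% (or greater) they give lower bounds of 52 (at most), 58, 64, 68 and 74% (at least). A footnote gives 54% as the upper confidence limit for remission in the placebo arm of HERCULES, in a post-hoc analysis. Neither document says how a non-integer responder count was handled.

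The planned analysis uses the same interval: "the proportion of responders will be calculated together with a 95% Wilson CI" (Protocol section 9.2.2). Section 9.4 also says that "no pre-specified success criterion and formal statistical hypothesis testing is planned".

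**The concern.** Putting the labelled rates straight into the Wilson formula at n=55 does not return the printed values in three of the five rows, and all three printed values are higher. With no hypothesis test, this precision statement is the only quantitative basis given for 55 participants, so its figures should match their labels.

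The wording is a separate matter. A confidence bound is a function of the observed count. To say that a true rate of 70% would give a bound of 58% presents one possible result as the expected one and leaves out sampling variation.

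**Working it through.** **Inputs.** n = 55; two-sided 95% Wilson interval, z = 1.96; rates 65, 70, 75, 80 and 85% (Protocol section 9.4 and Table 7; SAP section 4 and Table 6).

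**Formula.** L = [p + z²/(2n) − z·√(p(1−p)/n + z²/(4n²))] / (1 + z²/n). With n = 55: z²/(2n) = 0.0349, z²/(4n²) = 0.000317, 1 + z²/n = 1.0698.

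**Step 1: reproduce the printed 58%.** 55 × 0.70 = 38.5, rounded up to 39. With p = 39/55 = 0.7091, the numerator is 0.7440 − 0.1250 = 0.6190, and L = 0.6190/1.0698 = 57.9%, which rounds to 58%. The same rule reproduces every row, as the fifth column of the table below shows.

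**Step 2: use the labelled rates.** At p = 0.70 the numerator is 0.7349 − 0.1260 = 0.6089, and L = 56.9%. At p = 0.75 it is 0.7849 − 0.1196 = 0.6653, and L = 62.2%.

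| Label | 55 × rate | Count rounded up | Its exact rate | Bound at that count | Printed | Bound at the label |
|---|---|---|---|---|---|---|
| 65% | 35.75 | 36 | 65.5% | 52.3% | 52% | 51.8% |
| 70% | 38.5 | 39 | 70.9% | 57.9% | 58% | 56.9% |
| 75% | 41.25 | 42 | 76.4% | 63.7% | 64% | 62.2% |
| 80% | 44 | 44 | 80.0% | 67.6% | 68% | 67.6% |
| 85% | 46.75 | 47 | 85.5% | 73.8% | 74% | 73.3% |

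Comparing unrounded with unrounded, the 70, 75 and 85% rows are high by about 0.9, 1.5 and 0.5 points. The 65% and 80% rows are correct as printed under either reading.

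**Step 3: would rounding to the nearest participant rescue the table?**
- 65% and 85%: the nearest counts are 36 and 47, those behind the printed values.
- 70%: 38.5 is an exact tie. 38/55 (69.1%) gives 56.0% and 39/55 gives 57.9%.
- 75%: 41.25 is nearest to 41. 41/55 (74.5%) gives 61.7%, which rounds to 62%. The printed 64% needs 42/55.

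Only the 75% row fails this test outright.

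**Step 4: what a true 70% implies.** With X ~ Binomial(55, 0.70), a bound that rounds to 58% or more needs X ≥ 39, and P(X ≥ 39) = 0.51. The expected lower bound is 57.0%. The 10th to 90th percentile range is 48.6% to 65.6% (34/55 to 43/55). With a true 75% the expected bound is 62.3%.

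**The case against.** The strongest reply is that nothing was miscalculated. The Wilson formula was applied correctly to whole participants, whereas 56.9% and 62.2% correspond to 38.5 and 41.25 responders, which cannot be observed. At a true 70%, 39 is both the median and the most likely count, so 58% is a fair summary of the typical result; at 85%, 47 is the nearest count. Quoting a bound for an assumed rate is ordinary planning shorthand.

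Most of this stands. It defends the 70% row as a median result and the 85% row as nearest-count rounding. It does not defend the 75% row. There, 42 ties with 41 as the most likely count, but 41 is both the median and the nearest count, and the 62.3% expected bound also rounds to 62%. Nor does it supply the missing statement of the convention, or make the labels 70, 75 and 85% agree with the rates actually used.

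A reader might go further and infer that the sample size is too small because 58% is not reached at exactly 70%. The documents do not support that: 58% is a description of precision, not a target. A reader might also infer that the comparison with 54% is undermined. Under either convention the rows from 70% upward lie above 54% and the 65% row lies below it.

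**Conclusion.** The point holds as a labelling and disclosure fault with one clearly wrong row. Three of five rows are more favourable than their labels, by about 0.5 to 1.5 points, because counts were rounded up without saying so. The 75% row should read 62%. The 58% should be presented as the bound for an observed 39/55, which is reached or exceeded about half the time if the true rate is 70%.

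This assumes exactly 55 evaluable participants and a Wilson interval without continuity correction. That version, with counts rounded up, reproduces all five printed values. The rounding rule is inferred from that match, since the documents do not state one.

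The consequence is limited. The planned analysis is unaffected, and no success criterion or test uses the table. The 54% figure is a footnote reference for remission in an arm that received TPE, which is a different endpoint from remission without requiring TPE, so it should not be read as a threshold.

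**What to change.** In the synopsis, Protocol section 9.4 with Table 7, and SAP section 4 with Table 6, do one of the following:

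- keep the rate labels and restate the bounds as 52, 57, 62, 68 and 73%; or
- label the rows by observed result, 36, 39, 42, 44 and 47 of 55, with exact rates of 65.5, 70.9, 76.4, 80.0 and 85.5%, and keep the printed bounds.

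Under either option, describe the rates as observed rather than true, and make the 70% sentence agree with the table. One added sentence would cover sampling variation: at a true 70% the expected lower bound is 57.0%, and 39/55 or better has probability about 0.51. The chance of a bound above 54% at a true 70% (37/55 or more, about 0.73) could be added, but this is optional because 54% is not a criterion and refers to another endpoint.

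The cost is a text correction in two documents and, under the first option, slightly less favourable stated figures. It needs no more participants and no change to the analysis.

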10 SUPPORTING DOCUMENTATION AND OPERATIONAL CONSIDERATIONS

10.1 APPENDIX 1: REGULATORY, ETHICAL, AND STUDY OVERSIGHT CONSIDERATIONS

10.1.1 Regulatory and ethical considerations

- This study will be conducted in accordance with the protocol and with the following:
 - Consensus ethical principles derived from international guidelines including the Declaration of Helsinki and the applicable amendments and Council for International Organizations of Medical Sciences (CIOMS) international ethical guidelines
 - Applicable ICH Good Clinical Practice (GCP) guidelines
 - Applicable laws and regulations (eg, data protection law as General Data Protection Regulation - GDPR)
- The protocol, protocol amendments, ICF, Investigator's brochure, and other relevant documents (eg, advertisements) must be submitted to an IRB/IEC by the Investigator and reviewed and approved by the IRB/IEC before the study is initiated.
- Any amendments to the protocol will require IRB/IEC approval before implementation of changes made to the study design, except for changes necessary to eliminate an immediate hazard to study participants.
- Protocols and any substantial amendments to the protocol will require health authority approval prior to initiation except for changes necessary to eliminate an immediate hazard to study participants.
- The Investigator will be responsible for the following:
 - Providing written summaries of the status of the study to the IRB/IEC annually or more frequently in accordance with the requirements, policies, and procedures established by the IRB/IEC
 - Determining whether an incidental finding (as per Sanofi policy) should be returned to a participant and, if it meets the appropriate criteria, to ensure the finding is returned (an incidental finding is a previously undiagnosed medical condition that is discovered unintentionally and is unrelated to the aims of the study for which the tests are being performed). The following should be considered when determining the return of an incidental finding:
 - The return of such information to the study participant (and/or his/her designated healthcare professional, if so designated by the participant) is consistent with all applicable national, state, or regional laws and regulations in the country where the study is being conducted, and
 - The finding reveals a substantial risk of a serious health condition or has reproductive importance, AND has analytical validity, AND has clinical validity.

- The participant in a clinical study has the right to opt out of being notified by the Investigator of such incidental findings. In the event that the participant has opted out of being notified and the finding has consequences for other individuals, eg, the finding relates to a communicable disease, Investigators should seek independent ethical advice before determining next steps.
- In case the participant has decided to opt out, the Investigator must record in the site medical files that she/he does not want to know about such findings.
- Notifying the IRB/IEC of SAEs or other significant safety findings as required by IRB/IEC procedures
- Providing oversight of the conduct of the study at the site and adherence to requirements of 21 CFR, ICH guidelines, the IRB/IEC, European regulation 536/2014 for clinical studies (if applicable), European Medical Device Regulation 2017/745 for clinical device research (if applicable), and all other applicable local regulations

As applicable, according to Directive 2001/20/EC, the Sponsor will be responsible for obtaining approval from the Competent Authorities of the EU Member States and/or Ethics Committees, as appropriate, for any amendments to the clinical trial that are deemed as “substantial” (ie, changes which are likely to have a significant impact on the safety or physical or mental integrity of the clinical trial participants or on the scientific value of the trial) prior to their implementation.

10.1.2 Financial disclosure

Investigators and sub-Investigators will provide the Sponsor with sufficient, accurate financial information as requested to allow the Sponsor to submit complete and accurate financial certification or disclosure statements to the appropriate regulatory authorities. Investigators are responsible for providing information on financial interests during the course of the study and for 1 year after completion of the study.

10.1.3 Informed consent process

- The Investigator or his/her representative will explain the nature of the study, including the risks and benefits, to the participants or their legally authorized representative (refer to [Section 10.8.1](#) for country specific requirements for Germany), and answer all questions regarding the study, including what happens to the participant when his/her participation ends (post-trial access strategy for the study).
- Participants must be informed that their participation is voluntary. Participants or their legally authorized representative (refer to [Section 10.8.1](#) for country specific requirements for Germany) will be required to sign a statement of informed consent that meets the requirements of 21 CFR 50, local regulations, ICH guidelines, Privacy and Data Protection requirements including those of the Global Data Protection Regulation (GDPR) and of the French law, and Health Insurance Portability and Accountability Act (HIPAA) where applicable, and the IRB/IEC or study center.
- The medical record must include a statement that written informed consent was obtained before the participant was enrolled in the study and the date the written consent was obtained. The authorized person obtaining the informed consent must also sign the ICF.

- In case of ICF amendment while the participants are still included in the study, they must be re-consented to the most current version of the ICF(s). Where participants are not in the study anymore, teams in charge of the amendment must define if those participants must or not re-consent or be informed of the amendment (eg, if the processing of personal data is modified, if the Sponsor changes, etc.).
- A copy of the ICF(s) must be provided to the participant or their legally authorized representative (refer to [Section 10.8.1](#) for country specific requirements for Germany), where applicable.

Participants who are rescreened are required to sign a new ICF.

The ICF contains 2 separate sections that addresses the use for research of participants' data and/or samples (remaining mandatory ones or new extra samples collected for optional research). Optional exploratory research must be detailed in the section "Optional tests/procedures" and future research is to be defined in Core Study Informed Consent Form (CSICF) Part 2. Each option is subject to an independent consent and must be confirmed by ticking a checkbox in CSICF Part 3. The Investigator or authorized designee will explain to each participant the objectives of the exploratory research and why data and samples are important for future research. Participants will be told that they are free to refuse to participate and may withdraw their consent at any time and for any reason during the storage period.

For a regional or national emergency declared by a governmental agency, contingency measures are included in Appendix 9 ([Section 10.9](#): Contingency measures for a regional or national emergency that is declared by a governmental agency).

10.1.4 Data protection

All personal data collected and/or processed in relation to this study will be handled in compliance with all applicable Privacy & Data Protection laws and regulations, including the GDPR (General Data Protection Regulation). The study Sponsor is the Sanofi company responsible for ensuring compliance with this matter, when processing data from any individual who may be included in the Sanofi databases, including trial participants, Investigators, nurses, experts, service providers, Ethics Committee members, etc.

When archiving or processing personal data pertaining to the Investigator and/or to the participants, the Sponsor takes all appropriate measures to safeguard and prevent access to this data by any unauthorized third party.

Protection of participant personal data

Data collected must be adequate, relevant and not excessive, in relation to the purposes for which they are collected. Each category of data must be properly justified and in line with the study objective.

Participant race and ethnicity will be collected in this study because they are expected to modify the drug response/because they are required by regulatory agencies (eg, on African American population for the FDA or on Japanese population for the Pharmaceuticals and Medical Devices Agency in Japan). They will not be collected in the countries where this is prohibited by local regulation.

- Participants will be assigned a unique identifier by the Sponsor. Any participant records or datasets that are transferred to the Sponsor or its service providers, when applicable, will be identifiable only by the unique identifier; participant names or any information which would make the participant identifiable will not be transferred to the Sponsor.
- The participant must be informed that his/her personal study-related data will be used by the Sponsor in accordance with applicable data protection laws. The level of disclosure must also be explained to the participant as described in the informed consent.
- The participant must be informed that his/her medical records may be examined by Clinical Quality Assurance auditors or other authorized personnel appointed by the Sponsor, by appropriate IRB/IEC members, and by inspectors from regulatory authorities.
- Participants must be informed that their study-related data will be used for the whole “drug development program”, ie, for this trial as well as for the following steps necessary for the development of the investigational product, including to support negotiations with payers and publication of results.

Protection of personal data related to professionals involved in the study

- Personal data (eg, contact details, affiliation(s) details, job title and related professional information, role in the study, professional resume, training records) are necessary to allow Sanofi to manage involvement in the study and/or the related contractual or pre-contractual relationship. They may be communicated to any company of the Sanofi group (“Sanofi”) or to Sanofi service providers, where needed.
- Personal data can be processed for other studies and projects. At any time, objection to processing can be made by contacting the Sanofi Data Protection Officer (link available at Sanofi.com).
- In case of refusal to the processing of personal data by or on behalf of Sanofi, it will be impossible to involve the professionals in any Sanofi study. In case the professionals have already been involved in a Sanofi study, they will not be able to object to the processing of their personal data as long as they are required to be processed by applicable regulations. The same rule applies in case the professionals are listed on a regulatory agencies disqualification list.
- Personal data can be communicated to the following recipients:
 - Personnel within Sanofi or partners or service providers involved in the study,
 - Judicial, administrative and regulatory authorities, in order to comply with legal or regulatory requirements and/or to respond to specific requests or orders in the framework of judicial or administrative procedures. Contact details and identity may also be published on public websites in the interest of scientific research transparency.
- Personal data may be transferred towards entities located outside the Economic European Area, in countries where the legislation does not necessarily offer the same level of data protection or in countries not recognized by the European Commission as offering an adequate level of protection. Those transfers are safeguarded by Sanofi in accordance with the requirement of European law including, notably:
 - The standard contractual clauses of the European Commission for transfers towards our partners and service providers,
 - Sanofi’s Binding Corporate Rules for intra-group transfers.

- Professionals have the possibility to lodge a complaint with Sanofi leading Supervisory Authority, the “Commission Nationale de l’Informatique et des Libertés” (CNIL) or with any competent local regulatory authority.
- Personal data of professionals will be retained by Sanofi for up to thirty (30) years, unless further retention is required by applicable regulations.
- In order to facilitate the maintenance of Investigators personal data, especially if they contribute to studies sponsored by several pharmaceuticals companies, Sanofi participates in the Shared Investigator Platform (SIP) and in the TransCelerate Investigator Registry (IR) project (<https://transceleratebiopharmainc.com/initiatives/investigator-registry/>). Therefore, personal data will be securely shared by Sanofi with other pharmaceutical company members of the TransCelerate project. This sharing allows Investigators to keep their data up-to-date once for all across pharmaceutical companies participating in the project, with the right to object to the transfer of the data to the TransCelerate project.
- Professionals have the right to request the access to and the rectification of their personal data, as well as their erasure (where applicable) by contacting the Sanofi Data Protection Officer: Sanofi DPO - [name] (to contact Sanofi by email, visit <https://www.sanofi.com/en/our-responsibility/sanofi-global-privacy-policy/contact>).

